8.4 APX005M Infusion Procedure

APX005M solution for IV infusion may be administered by using an intravenous infusion pump using compatible IV bags, infusion sets, and materials.

The following IV solution containers and equipment have been evaluated for compatibility with APX005M by Apexigen. If a component of the infusion set-up planned for use is not listed in the table below, please contact Apexigen at [contact] to confirm acceptability of the component.

Prequalified Intravenous Equipment	
IV bag *, Normal Saline for Infusion	0.9% NaCl Viaflex 250 mL (PVC/DEHP) (Baxter P/N 2B1322Q)
IV tubing	Continuo-Flo® (Baxter P/N ACT8570)
IV Tubing	Paclitaxel® administration set (Baxter P/N 2CC8857)
IV Tubing/filter	Alaris Pump Infusion Set 0.2 Micron Filter (BD P/N 11532269)
* 50 mL or 100 mL IV bags are acceptable	

8.4.1 Inline filter (at least 0.2 micron)

All infusions must administered using an in-line low protein-binding filter (0.2 or 0.22 micron).

[figure not shown]
Figure 1: Example of Inline Filter (not to scale)

8.4.2 Inline 3-way stop-cock

A 3-way stock-cock immediately before the IV access device and distal (downstream) of the APX005M infusion solution insertion site is recommended. In the event of an infusion-related reaction, the infusion can be immediately interrupted and supportive medications and fluids maybe administered through the “flush” port.

Figure 2: Example of 3-way Stopcock

8.4.3 APX005M Infusion Using an Intravenous Infusion Pump

[figure not shown]
All IV preparation and infusion should be conducted under proper aseptic technique. Process steps with anticipated possible direct contact with APXM005 (e.g.: preparation and priming of APX005M) should include protective gloves. See Figure 3 for schematic of example IV infusion pump set-up.

Table 8: APX005M Administration Set-up (IV infusion Pump)

Step 1:	Assemble all equipment required for IV administration of APXM005
Step 2:	(Primary Line) Establish IV access with a primary IV line using Normal Saline for Injection; the primary IV line should be maintained at a KVO (keep vein open) rate. The purpose is to maintain constant low rate IV access
Step 3:	(Secondary Line) Using aseptic technique, puncture the IV infusion solution bag with the IV tubing (with built-in or added in-line low protein-binding 0.2 micron filter) and carefully prime the tubing and in-line filter to displace all air being careful not to waste any IV infusion solution
Step 4:	The secondary IV line (APX005M) should be connected as close the subject as possible. If using primary infusion tubing set with more than one injection port, use the most distal injection port. If using a 3-way stop-cock ensure that the stop-cock is as proximal to the subject as possible
Step 5:	Connect the primed IV tubing
Step 6:	Initiate the infusion at a rate intended to deliver the entire dose in approximately one hour.

	
 • Infusion is recommended to be 60 minutes (-5 to +10 minutes; i.e. 55 to 70 minutes) • Infusion may be interrupted for infusion-related reactions • Infusion is recommended to last no longer than 90 minutes • Infusion duration of > 90 minutes is acceptable based on subject tolerance but one should attempt to infuse within 60 to 90 minutes
Step 7:	Monitor for safety and tolerability
Step 8:	When IV infusion solution bag is empty, replace with second IV bag of plain NS
Step 9:	Continue infusion until sufficient amount of plain NS has been infused to ensure complete study drug administration (included in the 60-minute infusion period)
Step 10:	At completion of infusion and flushing procedure, remove the secondary IV tubing equipment and dispose of appropriately

Figure 3: Schematic IV infusion Setup with IV infusion Pump

8.5 Agent Ordering and Agent Accountability

8.5.1 Agent Ordering

The PBTC sites need to place an order for APX005M starter supplies upon site protocol activation. The shipment is anticipated to contain one-year supply for 2 subjects to minimize the amount of APX005M at member sites. For subsequent orders, sites are expected to request enough study drug to supply all potential patients for 6 months. Use the Apexigen Clinical Supply Shipment Request Form, which is posted on PBTC-051 webpage when ordering. Allow 7 business days from the request to receipt of APX005M.

Note: APX005M will not be shipped on Fridays.

Upon receipt, verify contents, complete drug acknowledgement form, and email back to Apexigen. Discrepancy or damage noted in the contents or if the shipment does not arrive within 7 business days, immediately notify Apexigen by the following addresses:

[contact]

[contact]

8.5.2 Agent Inventory Records and Accountability

The investigator, or a responsible party designated by the investigator, must maintain accurate records regarding study agent receipt, dispensing, use and disposal using the appropriate NCI Investigational Agent (Drug) Accountability Record (DARF). Store and maintain separate NCI Investigational Agent Accountability Records for each ordering investigator on this protocol. Records should include:

- Quantity of APX005M received and placed in storage area
- Quantity of APX005M currently in storage area
- APX005M label information
- Dates and initials of person responsible for each APX005M inventory entry/movement
- Quantity of APX005M administered to each subject. Documentation should include unique subject identifier
- Quantity of APX005M transferred to another area/site for dispensing or storage
- Non-study disposition of APX005M (e.g., lost, wasted, and/or broken)
- Quantity of APX005M destroyed at study site, if applicable
- Retention of used or partially used vials is not required.

8.5.3 Return and Destruction of APX005M

Upon completion or termination of the study, all unused APX005M can be destroyed at the site. It is the Investigator or designee's responsibility to dispose of all partial or empty containers, following procedures for proper disposal have been established according to applicable federal, state, local, and institutional guidelines and procedures. Appropriate records of disposal are to be maintained in the site pharmacy.

9 BIOMARKER, CORRELATIVE AND SPECIAL STUDIES

This section contains the collection, shipping and handling information for all planned biomarker and exploratory correlative studies. The table below identifies the tests, sample type and amount, analyzing laboratory and whether it is required or optional. For additional details, please review the associated section below.

Test Name	Sample Type and Amount	Analyzing Laboratory	Required or Optional	Section ID
Pharmacokinetics (PK)	Serum from 2 mL whole blood (3.5 mL serum tubes)	PPD	Required	9.1.2
Anti-Drug Antibody (ADA) Assay	Serum from 2 mL whole blood (3.5 mL serum tubes)	PPD	Required	9.1.2
T cell phenotyping	PBMC (minimal 16 mL blood, ideal 32 mL blood)	[name] MSKCC IMF	Required	9.1.4
Circulating Cytokines	(8 mL CPT tubes) Plasma	[name] MSKCC IMF	Required	9.1.3
Tumor Mutational Burden Assessment (Whole Exome Sequencing)	FFPE tumor tissue; PBMC (from 5 mL blood) (8 mL CPT tubes)	[name] Cleveland Clinic	Required	9.1.5
Repository Samples	PBMC and FFPE tumor tissue	PBTC	Optional	9.1.1

Blood sample prioritization: If there is limited blood samples to complete all mandatory assays, PK and ADA assays should be given priority.

9.1 Pathology and Exploratory Correlative Studies

The Pathology Central Review and Biorepository (CRB)'s function is to collect, distribute and store specimens for the planned correlative studies which support the laboratory objectives of this protocol.

The CRB will also serve as a central repository for specimens collected for future research and left over specimens (tumor tissue, blood) returned to the repository following the planned analysis from patients who consent to long term storage of unused specimen. These samples will be stored in the repository for undefined future studies which support the mission of the PBTC. **If the patient does not consent to participation in the repository, correlative study samples should be submitted following the guidelines in the appropriate correlative study section below. If the patient does not consent to long term storage, remaining correlative study samples will be destroyed once the PBTC-051 analysis is complete.**

9.1.1 PBTC CRB Submission Guidelines

If the patient consents to provide slides for submission to the repository at the time of participation in a PBTC trial the following should be submitted:

- Tumor material

Slides from the original and/or recurrent surgery should be prepared for storage. The site should provide up to twenty (20) unstained sections cut at 4µm in thickness on (+) slides from the most representative section. These submitted slides will be used for the conduct of studies outlined in section 9.1.5. Fewer unstained sections may be submitted based on size and availability of tissue. Preference is for tissue that has not previously been frozen. The corresponding pathology report (s) including immunohistochemical, special stains, and molecular/genetic results is to be

uploaded to the PBTC using the secure File Upload system. These reports will be made available to the pathologist via a link in the ProtoLab.

Suitability of sections would be established by preparing one (1) H&E to ensure that the sections meet the following criteria:

- histologically representative of the reported lesion
- contain at least 60% viable tumor
- no more than 40% necrosis

The following specimens may also be submitted to the CRB for distribution and storage:

- Scrolls: if sufficient tissue is available, 2 scrolls at 10 micron thickness as outlined in section 9.1.5
- Peripheral blood mononuclear cells: quantity and schedule of collection as outlined in section 9.1.4 and 9.1.5

- Peripheral Blood Mononuclear Cells

PBMC may be collected by processing a 2-5mL whole blood specimen with Ficoll or collecting the specimen in a BD Vacutainer™ CPT™ Cell Preparation Tube with Sodium Citrate or a similar tube which is available locally. Once separated, all pellets must be snap frozen and stored at least at -20°C prior to dry ice shipment

9.1.1.1 Specimen Collection and Processing by Ficoll tube

- Collect 2 - 5mL of fresh blood into an EDTA tube.
- Transfer blood into a sterile 50-mL tube and add double the amount of PBS. MIX GENTLY.
- Set up another tube containing half of its total volume of Ficoll. For example, if there is 15 mL of blood + PBS, then use 7.5 mL of Ficoll (2:1 ratio).

At very slow pace (approx. 2 mL/minute), layer the blood + PBS mixture onto the Ficoll so that the solutions DO NOT MIX. Spin the blood/Ficoll at 750 g in slow mode for 30 minutes @ 25°C. After spin you will see four distinct layers: plasma (top layer), white fluffy ring (2nd layer), Ficoll (3rd layer), and blood (bottom layer).

- Remove plasma layer down to about 1 mL above the white fluffy ring and discard.
- Collect the entire white fluffy ring. If ring is hard to see, also take extra liquid above. Then discard everything else.
- Place this fraction of white blood cells into a fresh 50 mL sterile tube with 20 mL of PBS. Spin down for 10 minutes @ 25°C, 750 g in fast mode. Remove the supernatant. Add back to pellet 1 mL of PBS and spin for 5 min. at 4°C at 10000rpm. Remove supernatant.
- Freeze the pellet of WBCs in cryovials that are 2 mL or smaller and store at -80°C until shipment.
- Ensure that all tubes are clearly labeled with the PBTC patient accession number, sample type, collection date and Study ID. Please ensure that the labeling system used is designed to withstand temperatures down to -80°C. Samples should be stored at -80°C until shipment. For short term storage (2-3 weeks) -20°C is acceptable. NOTE 4°C IS NOT ACCEPTABLE STORAGE.

If it is not possible to collect the PBMC by Ficoll gradient then separation of PBMC can be conducted using CPT tube separation as an alternative. However the PBMC pellet **MUST BE** frozen immediately and stored at -80°C.

9.1.1.2 *Collection and Processing by CPT tube*

- Peripheral blood should be collected in a BD Vacutainer CPT™ Cell Preparation Tube with Sodium Citrate or similar tube which is available locally. 8 mL and 4 mL CPT tubes can be obtained from Fisher Scientific (Cat# 02-685-125, 02-688-81) or Becton-Dickinson (BD No.362761, 362760). The 8 mL tubes have a 6 mL minimum draw and the 4 mL tubes have a 3 mL minimum draw.
- Centrifuge the CPT™ tube at 1500 x g for 30 minutes at room temperature (20° C to 25° C). **DO NOT APPLY THE BREAK ON THE CENTRIFUGE.** Use acceleration 5, brake 0 (“slow mode”).
- It may be necessary to spin the tube longer to ensure that all of the red blood cell components have been separated from the plasma layer through the polyester gel barrier.
- The tube should be removed immediately from the centrifuge. The mononuclear layer and plasma lie above the polyester gel plug.
- Using a sterile pipette, remove as much of the plasma component (upper half of the CPT tube) without disturbing the mononuclear layer if possible and discard.
- Transfer mononuclear cell layer (and some residual plasma layer) to a labeled 15- mL conical centrifuge tube and add 5 mL sterile room temperature magnesium or calcium-free phosphate buffered saline (PBS) to fill the conical tube and recap.
- Centrifuge at 450 x g for 10 minutes at room temperature (20° C to 25° C). Use acceleration 9, brake (“fast mode”).
- Remove supernatant, being careful not to aspirate the cellular pellet at the bottom of the tube.
- Add 1 mL of sterile PBS to the pellet and gently re-suspend by pipetting up and down. Transfer the entire suspended pellet to the labeled cryovial that is 2 mL or smaller.
- Centrifuge the cryovial at 450 x g for 5 minutes (or spin down the microcentrifuge tube at 1300 x g for 5 minutes) at room temperature. Discard the supernatant. Store the cell pellet cryovial frozen at -80°C. For short term storage (2-3 weeks) -20° C is acceptable.

9.1.1.3 *Handling of Specimens*

- Slides are to be labeled with the study ID and the patient PBTC Accession # and these slides should be designated as PBTCR # (where the # assigned from 1 to 20, or the highest number of unstained sections prepared, sequentially) or PBTCR H&E for the H&E stained section.
- Scrolls or Formalin Fixed, Paraffin Embedded (FFPE) tumor materials are to be labeled with the PBTC Accession # and the PBTC study for which the sample is provided. Scrolls or FFPE tumor material should be shipped at room temperature.
- PBMCs are to be labeled with the PBTC Accession #, sample type, date of collection and the PBTC study ID for which the sample is provided. The PBMCs should be put in

cryovials that are 2 mL or smaller. Samples should be shipped overnight in a separate box with a 2-day supply of dry ice.

9.1.1.4 Shipment of Specimens

Samples collected for the repository should be sent to the PBTC CRB overnight via FedEx by completing the Internet form at <http://www.fedex.com/us/> and requesting FedEx to e-mail listed below. FedEx user ID and password for pathology shipping can be found at PBTC-051 protocol webpage. Samples should be shipped in the appropriate environment as described in Section 9.1.1. Samples are to be shipped to:

PBTC CRB

Research Support and Biorepository Services
Children's Hospital Los Angeles

[REDACTED]
[REDACTED]
[REDACTED]
[REDACTED]

Email: [contact]

9.1.2 Pharmacokinetics (PK) and Anti-Drug Antibody (ADA) assays

Pharmacokinetics (PK) and Anti-Drug Antibody (ADA) studies will be obtained from all patients enrolled on this study.

9.1.2.1 Collection of Specimens

Sampling Strategy for Pharmacokinetic Study

Course 1 and 2: serial blood samples for APX005M pharmacokinetic studies will be collected at the following times: pre-dose, at the end of infusion, and at 4, 24 ± 1 (Day 2), and 168 ± 4 hours (Day 8) from the start of the infusion in that course.

Course 3 and 4: serial blood samples for APX005M pharmacokinetic studies will be collected at pre-dose and at the end of infusion.

Sampling Strategy for ADA Assays

Serial blood samples for Anti-APX005M antibodies (ADA) will be collected prior to dosing on Course 1, 2, 3, 4, then every 3rd Course (Course 7, 10), and then every 4 courses (Course 14, 18, 22, 26, 30, 34) till the end of therapy (EOT) visit.

9.1.2.2 Handling of Specimens

At each time point, two tubes of 2 mL of blood (one for PK, another for ADA assay) will be collected into serum tubes such as BD366431 or 366430 which are appropriately labeled. The PK and ADA sample collection form should be completed with the exact time that the sample is drawn as well as the exact time that the drug is administered. The PK and ADA sample collection form is located on the PBTC-051 webpage. The samples should be labeled with the PBTC Accession number and the Course, Day and Time information for each sample.

Here is the instruction for serum processing:

Blood must not be drawn from the intravenous line used for infusion and should not be drawn from any indwelling venous access device proximal to the infusion site. For PK and ADA assays, please collect one serum sample for PK and one serum sample for ADA assay at each designated time point.

- 1) Allow vacutainer to fill completely
- 2) Gently invert the vacutainer approximately 5 times to allow complete mixing of additive
- 3) Allow sample to clot at room temperature
- 4) Centrifuge to separate the clot from the serum (refrigerated centrifuge is recommended but not required)
 - a. Spin at 1200g for 10 minutes
- 5) Remove the stopper of the vacutainer
- 6) Using a pipette, aliquot into 2 polyethylene freezer storage tubes (approx. 0.25 mL/tube)
- 7) Ensure that the samples are properly labeled with Subject ID Number, protocol-specified time point, date of collection, and time of collection.
- 8) Place properly labeled aliquots in – 70/-80° C freezer until shipment. (Ensure sample is fully frozen prior to packaging and shipping)

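### Section 9.1.2.2 calls for a PK and an ADA tube at every time point, but 9.1.2.1 schedules ADA before dosing only: 28 tubes against 18 in Courses 1-4

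*Combined protocol and SAP*

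**What the plan says.** **Timing, section 9.1.2.1 (Collection of Specimens).** Courses 1 and 2 each have five PK samples: "pre-dose, at the end of infusion, and at 4, 24 ± 1 (Day 2), and 168 ± 4 hours (Day 8) from the start". Courses 3 and 4 have two each, one before the dose and one when the infusion ends. No PK sample is listed after Course 4. The ADA rule is different: "Serial blood samples for Anti-APX005M antibodies (ADA) will be collected prior to dosing on Course 1, 2, 3, 4". Later ADA draws fall at Courses 7 and 10 and then at four-course intervals from Course 14 up to Course 34, closing with an end-of-therapy visit. Every ADA draw with a named course is a pre-dose draw.

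**Timing, section 9.1.2.2 (Handling of Specimens).** "At each time point, two tubes of 2 mL of blood (one for PK, another for ADA assay) will be collected". The serum-processing text in the same section repeats that one PK and one ADA sample are taken at each designated time point.

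**Volume.** Section 9.1.2.2 gives 2 mL per tube, and the first step of its processing list is "Allow vacutainer to fill completely". It names two catalogue tubes as examples without giving their capacity. The table at the start of section 9 has the same entry for both assays: "Serum from 2 mL whole blood (3.5 mL serum tubes"). Section 9.1.2.1 gives no volume, and the table gives no ADA timing.

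**Study calendar (section 10).** It marks both assays as required. Its footnote F refers the reader back to section 9.1 for the schedule, so it does not settle the conflict. It does mark an ADA sample, but no PK sample, at completion or off treatment.

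**The concern.** The two subsections give different instructions for the same visit. At end of infusion, 4 hours, 24 hours and Day 8, 9.1.2.1 asks for a PK tube alone and 9.1.2.2 asks for two tubes. At the ADA visits after Course 4 the conflict runs the other way: 9.1.2.1 asks for an ADA tube alone, and 9.1.2.2 read literally adds a PK tube that no schedule lists.

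What is at stake is blood taken from children and consistency between sites.

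- The minimum age is 1 year (3.1.3). Hemoglobin may be as low as 8 g/dL at entry, with transfusion allowed (3.1.9), and the laboratory limits must be met again before each course (5.1.3).
- A further 16 to 32 mL is drawn for T-cell phenotyping and cytokines before treatment and one week after the first dose (9.1.4.1), around the same time as PK draws. Safety bloods are weekly in Courses 1-2.
- When blood is short, section 9 gives PK and ADA priority. An unscheduled ADA tube could therefore displace a required cytokine or T-cell sample.
- The ADA objective (1.3.1) is incidence. The pre-dose schedule was written to serve it, and the documents state no purpose for post-dose ADA samples.

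**Working it through.** The documents state no total blood volume, so there is no figure of the plan's own to reproduce. The check is a count of tubes times volume.

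**Inputs**

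- PK time points (9.1.2.1): 5 in each of Courses 1 and 2, 2 in each of Courses 3 and 4.
- ADA time points (9.1.2.1): 1 in each of Courses 1-4, then Courses 7, 10, 14, 18, 22, 26, 30 and 34 (8 visits), plus end of therapy.
- Volume per tube: 2 mL (9.1.2.2 and the section 9 table).
- Tube size: 3.5 mL (section 9 table only).

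**Courses 1-4, tubes**

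- PK time points: 5 + 5 + 2 + 2 = 14.
- Schedule in 9.1.2.1: 14 PK + 4 ADA = 18 tubes.
- Paired draw in 9.1.2.2: 14 × 2 = 28 tubes.
- Difference: 28 − 18 = 10 ADA tubes with no place in the schedule.

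**Courses 1-4, volume**

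| Reading | 2 mL per tube | 3.5 mL tubes, filled |
|---|---|---|
| 9.1.2.1 schedule (18 tubes) | 18 × 2 = 36 mL | 18 × 3.5 = 63 mL |
| 9.1.2.2 paired draw (28 tubes) | 28 × 2 = 56 mL | 28 × 3.5 = 98 mL |

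At the stated 2 mL the ratio is 56 / 36 = 1.56, an extra 20 mL. The right-hand column applies only if the 3.5 mL tubes of the section 9 table are used and the fill step is followed literally.

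**By course, at 2 mL**

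- Courses 1 and 2, each: (5 + 1) × 2 = 12 mL against 5 × 2 × 2 = 20 mL.
- Courses 3 and 4, each: (2 + 1) × 2 = 6 mL against 2 × 2 × 2 = 8 mL.
- Check: 12 + 12 + 6 + 6 = 36 and 20 + 20 + 8 + 8 = 56.

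**After Course 4, at 2 mL**

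Section 9.1.2.1 lists 8 ADA visits plus end of therapy, 9 tubes or 18 mL. The paired reading adds 9 PK tubes, another 18 mL, for a patient who completes the schedule.

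**Serum kept**

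Section 9.1.2.2 keeps two aliquots of about 0.25 mL, so about 0.5 mL per tube. The volume that either assay needs is not stated.

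**The case against.** **A site may never be misled.** Section 9.1.2.1 is the subsection on collection and 9.1.2.2 the one on handling. Footnote F of the calendar points to section 9.1 for the schedule. There is also a PK and ADA collection form, which is not in the documents and may list the right tubes at each visit. The repeated sentence in 9.1.2.2 speaks of designated time points, which could mean each assay at its own times. This has some weight, but the first sentence in 9.1.2.2 leaves little room for the milder reading, and a form should not have to correct the protocol.

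**The effect is modest.** At 2 mL the excess is 20 mL over four courses. Stratum 1 has finished accrual, and only Stratum 2, with about 12 evaluable patients, is still enrolling. No endpoint, estimate or dose decision changes. All of this stands, and it limits the point to a correction of text.

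**Stronger readings that the documents do not support.**

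- A reader might combine the paired draw with full 3.5 mL tubes and conclude that children give up to 98 / 36 = 2.7 times the specified blood. That needs every tube to be a filled 3.5 mL tube, although 9.1.2.2 itself states 2 mL and the capacity of its two example tubes is not given. Nor is 2.7 a ceiling: on the same assumption Course 1 alone gives 35 / 12 = 2.9.
- A reader might say that the excess is over what the assays need. The 36 mL is the specified collection volume; no assay requirement is given.
- A reader might argue that ADA results from post-dose samples are hard to interpret because drug is circulating. That depends on assay properties that the documents do not describe.
- A reader might ask for a PK tube at each later ADA visit so that ADA can be read against drug level. The objective is incidence only, so this is a separate design preference.
- A reader might express the draws as a share of a small child's blood volume. The documents give no weight or blood volume. The 5 mL for sequencing may also overlap the phenotyping draw, since 9.1.5.1 refers to 9.1.4.1 for its collection.

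**Conclusion.** The conflict is real and should be corrected. Section 9.1.2.2 contradicts the ADA schedule in 9.1.2.1 and, followed as written, changes what is drawn from patients: 10 extra ADA tubes in Courses 1-4 and 56 mL instead of 36 mL. Those figures use only the stated time points and the stated 2 mL, and assume a patient who completes four courses. Most of the excess falls in Courses 1 and 2, at 8 mL each.

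The volume instructions are a second, smaller inconsistency. A 2 mL draw, a 3.5 mL tube and a complete fill cannot all hold. The 63 mL and 98 mL totals show what could follow, but they are conditional on the tube size in the section 9 table.

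Neither matter affects the dose-finding or efficacy conclusions.

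**What to change.** 1. In 9.1.2.2, replace both sentences that pair the tubes with: *Draw the PK tube at the PK time points and the ADA tube only at the ADA time points listed in 9.1.2.1.* This also settles the visits after Course 4, where 9.1.2.1 lists ADA without PK.
2. Make draw volume, tube size and fill step agree across 9.1.2.2 and the section 9 table: either replace the fill step with an instruction to draw 2 mL, or name a 2 mL tube in both places.
3. Say in 9.1.2.1 that an ADA sample is taken at the end-of-therapy visit, as the calendar marks it.
4. Check that the PK and ADA collection form matches.

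The cost is a short wording amendment and a check of one form. No scheduled sample is lost. Compared with 9.1.2.2 as written, a patient who completes four courses gives 20 mL less blood.
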